#### **6.9.2.1.1 Deviations, missing concentrations and anomalous values**

In all PK and PD summary tables and plots, plasma concentrations will set to missing if one of the following cases is true:

1. A concentration has been collected as not done (ND) or no sample (NS);
2. A deviation in sampling time is of sufficient concern or a concentration has been flagged anomalous by the pharmacokineticist. These deviations will be defined at the Data Review Meeting.

Note: summary statistics will not be presented at a particular time point if more than 50% of the data are missing.

All concentrations BLQ will be set to half the value of the LLQ for calculation of concentration summary statistics. However, in the listings BLQ values will be reported as "<LLQ", where LLQ will be replaced with the corresponding value for the LLQ.

#### **6.9.2.2 PK Parameters**

The following PK parameters will be derived, where appropriate, from the PK and PD Analysis Set of plasma concentration-time C1INH data using non-compartmental procedures.

Table 7 defines the PK parameters which will be calculated in this study.

**Table 7 PK Parameter Definitions**

Parameter	Definition
$C_{max}$	Peak concentration of C1INH.
$AUC_{0-3}$	Area under the plasma concentration-time curve from Presentation to 3 hours post-infusion.

Table 7 refers to the timepoint 3 hours for  $AUC_{0-3}$ . This is identical to the timepoint 2-4 hours in Table 2: Study Visits. In all summaries the 2-4 hours label will be used rather than 3 hours.

Actual PK and PD sampling times will be used in the derivation of PK parameters and will be calculated as follows:

All concentrations BLQ will be set to half the value of the LLQ for calculation of PK parameters.

AUC(0-3) will be calculated using the linear-up log-down trapezoidal method.

$C_{max}$  will be calculated by taking the maximum C1INH concentration for a patient's first attack. It will only be calculated if there are three measurements for all three time points.

If a PK parameter cannot be derived from a patient's concentration data, the parameter will be coded as NC (i.e. not calculated). Note: NC values will not be generated beyond the time that a patient discontinues.

In summary tables, statistics will be calculated by setting NC values to missing; and statistics will not be presented if more than 50% of the data are NC.

If an individual patient has a known biased estimate of a PK parameter (e.g. due to an unexpected event), this will be footnoted in the summary tables and will not be included in the calculation of summary statistics. Biased estimates will be identified and listed during the Data Review Meeting alongside a review of the protocol deviations prior to database lock.

The summary of PK parameters will include the following statistics: n, mean, geometric mean, median, SD, coefficient of variation (CV) Geometric CV, minimum and maximum.

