8 TREATMENT OF PATIENTS

8.1 Intervention

Patients up to 84 kg will receive one i.v. injection of Ruconest at a dose of 50 U/kg. The reconstituted solution should be administered as a slow i.v. injection over approximately 5 minutes. Patients of 84 kg body weight or greater will receive one i.v. injection of Ruconest at the dose of 4200 U (2 vials).

At the discretion of the investigator and depending upon the patient's clinical response, an additional dose may be given to patients following their initial dose as specified above. Not more than two doses should be administered within 24 hours.

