The treatment appeared safe and well-tolerated. No clinically significant AEs, changes in vital signs, safety laboratory parameters or antibody responses to C1INH or rabbit milk protein were observed. The PK findings from Study C1 1101-01 were confirmed in HAE patients treated with rhC1INH for an acute angioedema attack. Both patients and physicians evaluated treatment with rhC1INH as favorable compared to previous untreated attacks. The median time to the beginning of relief was 30 and 60 minutes, as reported by physicians and patients, respectively. The median time to minimal symptoms was 4 hours. All treated attacks resolved completely and no relapses occurred. No difference in response was observed on first and repeated treatments.

Study C1 1106-02

In Study C1 1106-02, fourteen healthy volunteers were enrolled to receive rhC1INH at 100 U/kg on five occasions with intervals of approximately 3 weeks between doses. Serial PK sampling was performed following the first, third and fifth administrations of rhC1INH. After administration of rhC1INH the levels of C1INH activity peaked at median times of about 20-30 minutes and thereafter declined to endogenous levels in about 8 to 12 hours. No difference in PK profiles was observed following the 1st, 3rd, and 5th administrations of rhC1INH.

One anaphylactic reaction occurred in an adult female participating in this study on first exposure to rhC1INH. This patient had a clinical history of rabbit allergy (not disclosed during the study pre-consent screening procedure). The patient was also subsequently found to have a clinically significant IgE antibody level against rabbit epithelium (dander) allergens.

No clinically significant changes in hematology, biochemistry, urinalysis, coagulation, vital signs or ECG parameters or physical examinations were noted in this study.

Study C1 1207

In Study C1 1207, an open-label exploratory phase II study, the safety and prophylactic effect of weekly administrations of rhC1INH was studied in asymptomatic HAE patients. Twenty-five patients were enrolled and treated with rhC1INH at 8 weekly administrations of 50 U/kg and followed up for 42 days after the last administration.

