10.2.1.3 Diagnostic tests, PK/PD and immunological analyses

Following collection, the samples will be kept and processed **at room temperature**. The eventual plasma aliquots should be immediately stored upright at or below -20 °C until shipment to QPS Netherlands BV, where sample analysis will be performed. Investigator manuals will be provided to each center detailing the procedures related to central laboratory sample handling and (dry ice) shipment.

Diagnostic assays

Blood samples for diagnostic assays will be collected at screening. The samples will be analyzed for the following parameters: C1INH activity, C1q, C4 and C1INH auto antibodies (IgM, and IgG anti-rhC1INH); C4 will also be analyzed at baseline of each attack.

PK/PD assays

Blood samples for PK assays will be collected prior to the first treatment, one blood sample directly following infusion (named T 5 min, from a vein in the contra-lateral arm) and another blood sample between 2-4 hours post-infusion. This sampling time points are considered the most useful schedule derived from modelling of adult data. The samples will be analyzed for C1INH activity and C4.

Immunogenicity

The presence of anti-C1INH IgG and IgM antibodies (tested against immobilized rhC1INH), and of antibodies against anti-HRI will be assessed. Cut-off values of each assay were previously determined using plasma samples from normal donors and hereditary angioedema patients not previously exposed to rhC1INH. Plasma samples found to have an antibody test result above the cut-off level of the assay will be tested in confirmatory assay(s):

- Plasma samples above cut-off for anti-C1INH antibody will be tested in an anti-C1INH displacement assay, to determine whether or not increased values observed in the ELISAs

Safety of Ruconest in 2-13 year old HAE patients

were due to specific or non-specific responses. Samples that are confirmed positive in the displacement assay will then be tested in an assay for neutralizing antibodies.

- Plasma samples that show a response above the cut-off level in the initial anti-HRI ELISA will be tested in a displacement assay.

These tests will be performed on samples obtained at screening, prior to each treatment with rhC1INH, and at the Day 28 and Day 90 follow up visits. If the new attack is treated before completing the follow-up visits for the previous attack, the D28 or D90 visit schedule will be reset based on the most recent treatment.

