### **3.6 Pharmacokinetic (PK)/Pharmacodynamic (PD) Analysis Set**

The PK/PD analysis set is defined as the subset of the Safety analysis set that has sufficient plasma concentration data. A patient will be seen as having sufficient plasma concentration data if at least the peak plasma concentration ( $C_{max}$ ) can be calculated.

All PK/PD analyses will be performed on the PK/PD analysis set.

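### C1INH Cmax is calculated only from complete three-sample profiles, so children with a valid 5-minute value can drop out of the Cmax summary and the PK/PD Analysis Set; the highest observed value is also labelled as the peak.

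*SAP*

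**What the plan says.** PK sampling is at the first attack only. Protocol 10.2.1.3 asks for a pre-treatment sample, "one blood sample directly following infusion (named T 5 min, from a vein in the contra-lateral arm"), and "another blood sample between 2-4 hours post-infusion". It adds: "This sampling time points are considered the most useful schedule derived from modelling of adult data".

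SAP Table 7 defines Cmax as "Peak concentration of C1INH". The text below the table takes the maximum C1INH value at the first attack and adds the condition "It will only be calculated if there are three measurements for all three time points". Otherwise Cmax is coded NC and treated as missing. Parameter statistics are withheld when more than half the values are NC.

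SAP 3.6 carries the condition into the analysis set: "A patient will be seen as having sufficient plasma concentration data if at least the peak plasma concentration" can be calculated. The same section assigns every PK/PD analysis to that set. SAP 3.5 defines a wider PK/PD Concentration Set (at least one measured concentration). SAP 6.9.2.1 and Table 14.2.2.1.1 use the wider set to list, summarise and plot concentrations by nominal time.

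SAP 7.1 acknowledges that there are too few sampling times for the protocol's full parameter list and retains only Cmax and AUC0-3.

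**The concern.** An AUC from Presentation to about 3 hours needs all three samples; a maximum does not. The SAP's Cmax is not baseline-corrected, so the Presentation value contributes nothing to it. After a single dose the 2-4 h value is expected to be well into the decline. The completeness rule can therefore make Cmax unavailable for a child whose informative sample was taken and assayed. PK is a secondary objective with a target of at least 20 treated children. SAP 6.9.2.1.1 also sets a value to missing in summaries when its sampling time deviates too far or it is flagged as anomalous, so losses are not confined to missed draws.

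The second issue is the label. Table 7 calls the result the peak without qualification, yet nothing is sampled between 5 minutes and 2 hours. The protocol argues from similar PK across age groups and quotes a Cmax of 1.36 U/mL at 50 U/kg from a study in asymptomatic HAE patients. A reader is likely to set the children's Cmax beside that figure.

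**Working it through.** The plan gives no figure to reproduce here: there is no formal sample size and no stated sample-loss rate.

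**1. Children kept under each rule.** N = 20 is the protocol's minimum number treated. The loss rate m per sample is an assumption, taken as independent across the three samples.

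- Three-sample rule: 20 × (1 − m)³
- 5-minute sample only: 20 × (1 − m)

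| m (assumed) | Three samples | 5-minute only | Valid 5-minute value but no Cmax |
|---|---|---|---|
| 5% | 17.1 | 19.0 | 1.9 |
| 10% | 14.6 | 18.0 | 3.4 |
| 15% | 12.3 | 17.0 | 4.7 |
| 20% | 10.2 | 16.0 | 5.8 |

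At 10%, 3.4/18 = 19% of usable 5-minute values yield no Cmax. If a child's losses always occurred together, the last column would be zero, so these are upper-end figures for a given m.

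**2. Suppression of the summary.** If the more-than-half-NC rule is applied to all 20 children, the binomial chance of 11 or more NC is below 0.1%, 0.8%, 10.2% and 37.0% at the four rates. It is below 0.1% throughout if only the 5-minute sample is needed. If the rule is applied within the PK/PD Analysis Set, Cmax can never be NC, because a calculable Cmax is the entry condition. The SAP does not say which denominator applies.

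**3. Could the 2-4 h sample set the maximum?** Inputs from Protocol 9.3 at 50 U/kg: peak 1.36 U/mL, and above 0.7 U/mL for about 2 h. Baseline b is varied from 0 to 0.3 U/mL; Protocol 4.1 gives about 20% of normal as the median in type I disease. Assume mono-exponential decline above baseline:

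C(t) = b + (1.36 − b)·exp(−kt), with k = ln[(1.36 − b)/(0.7 − b)]/2, so C(2) = 0.70 and C(4) = b + (0.7 − b)²/(1.36 − b).

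- b = 0: C(4) = 0.49/1.36 = 0.36
- b = 0.3: C(4) = 0.3 + 0.16/1.06 = 0.45

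A 5-minute value near the peak would be 1.36/0.70 = 1.9 to 1.36/0.36 = 3.8 times any 2-4 h value.

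**4. Stress test with a later peak.** Take b = 0.2, k = ln(1.16/0.5)/2 = 0.42 per hour, and an assumed first-order rise timed to peak at 1.36 U/mL:

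C(t) = 0.2 + 1.16·B(t)/B(T), with B(t) = exp(−kt) − exp(−at). For T = 20/25/30 min, a = 9.89/7.25/5.6 per hour.

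- At 5 min: 0.93/0.82/0.72 U/mL
- At 2 h: 0.80/0.83/0.87 U/mL
- At 4 h: 0.46/0.47/0.49 U/mL

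With so late a peak, a sample drawn close to 2 h could slightly exceed the 5-minute value. The model leans that way, since its 2 h level lies above the protocol's figure of about 0.7. At 4 h the 5-minute value is higher in every case.

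**5. Shortfall from the true peak.** This cannot be calculated. The documents give no time of peak for 50 U/kg injected over about 5 minutes.

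**The case against.** The strongest reply is that the 5-minute values are not lost. A reader might infer from the rule that they are thrown away. The documents do not support that: Table 14.2.2.1.1 and the C1INH boxplots use the PK/PD Concentration Set, so every valid 5-minute value is listed, plotted and summarised with its own n. This stands. It confines the point to the Cmax summary and the Analysis Set, and it means that replacing Cmax by a 5-minute concentration would largely duplicate an existing table row.

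A reader might also infer that the reported figure is not the peak, because Protocol 9.3 says: "After administration of rhC1INH the levels of C1INH activity peaked at median times of about 20-30 minutes". That figure comes from 14 healthy volunteers given 100 U/kg, with no infusion time stated. Here the dose is 50 U/kg up to 84 kg, and "The reconstituted solution should be administered as a slow i.v. injection over approximately 5 minutes". The 50 U/kg study in HAE patients gives a Cmax but no time of peak, and the schedule is said to come from modelling of adult data. An end-of-injection sample may be at or near the peak. Only the statement that the peak may be missed is supported.

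Other points on that side carry some weight. Table 7's wording can be read with the derivation below it, which makes clear that an observed maximum is meant. The loss rates are assumed; children stay at least 4 hours and a catheter is recommended, so missed samples may be few or clustered. A second dose before the 2-4 h sample could make that sample the maximum. No hypothesis test or adult comparison is planned. A single complete-profile set also gives Cmax and AUC0-3 the same n.

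None of this supplies a reason to require the Presentation sample for a maximum, or to let its absence decide entry to the Analysis Set.

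**Conclusion.** The point holds in a limited form. The three-sample condition removes children with a valid 5-minute value from the Cmax summary and the PK/PD Analysis Set. At assumed independent losses of 5% to 20% per sample, that is about 2 to 6 of 20 children, and fewer if losses cluster. Requiring Presentation adds nothing to a maximum. Requiring the 2-4 h sample adds nothing if the 5-minute value is near the peak. It could matter slightly if the peak comes late and the sample falls near 2 h, or if a second dose intervenes; flagging those children handles the second case.

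On the label, the reported Cmax is the highest observed concentration. It can equal or understate the true peak, by an unknown amount. The documents do not show that it does understate it.

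The analyses are descriptive and PK is a secondary objective, so no error rate or sample size is affected. This is an inexpensive improvement, not a flaw that undermines the PK results.

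**What to change.** - In SAP 6.9.2.2, calculate Cmax as the maximum observed C1INH concentration at the first attack for every child with a valid 5-minute sample. Keep a separate data requirement for AUC0-3.
- In SAP 3.6, base the PK/PD Analysis Set on a valid 5-minute sample. Reconcile the sentence assigning all PK/PD analyses to that set with the use of the Concentration Set in 6.9.2.1.
- In Table 14.2.2.1.2, show n for each parameter and flag children given a second dose before the 2-4 h sample. State the denominator for the more-than-half-NC rule.
- In Table 7, relabel Cmax as maximum observed concentration. Add a footnote that the true peak may be missed and that the value is not directly comparable with a Cmax from rich sampling.

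The cost is a few lines of SAP text and a rerun of one table on data already held. The drawback is that n may differ between Cmax and AUC0-3. The deviation form attached to the SAP says the analysis has been finalised, so the change would now be a disclosed and justified addition in the clinical study report, the route SAP 7.5 gives for changes after database lock.

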## 7. Changes to the Planned Analyses

### 7.1 Changes to the Analyses Described in the Study Protocol and Protocol Amendments

Due to an inadequate number of sampling time points; the only PK parameters calculated will be AUC0-3 and  $C_{max}$ . See Section 7.3 for further details.

### 7.2 Changes from the Statistical Analysis Plan Version 1.0.0

Clarification regarding the review of diary data for completion of the Day 28 CRF was made in Section 2.2. Section 6.8.6 was added to describe collection of routine physical examination data. Re-numbering of outputs in Attachment 1 was performed to bring tables, listings and figures in line with ICH E3 reporting guidelines. No changes were made to planned analyses.

### 7.3 Changes from the Statistical Analysis Plan Version 2.0.0

- The following updates were made to Version 2.0.0. of the SAP:
- Section 3.7 concerning analysis of subgroups was removed.
- Section 4.1 was updated throughout to give further detail on efficacy measures and ensure there are precise instructions for analysis.
- Section 4.2.1 had further detail added to clarify how certain exposure measures will be calculated.

- Section 4.2.2 was updated to better describe definitions of TEAEs and how AEs will be coded. Clarification was also given for how AEs should be linked to attacks.
- Section 4.2.3 was updated to clarify how lab measurements will be converted to standard units.
- Section 4.3.1 Was updated to include details of IgE testing.
- Section 4.3.2 was updated to highlight that AUC(0-3) and Cmax will be the only PK parameters calculated.
- Section 4.3.3 was updated with a more detailed description of the immunogenicity study procedures.
- Section 4.3.5 was updated to better reflect the determination of protocol violations. A list of inclusion and exclusion criteria was removed from this section.
- Section 4.3.7.1 and 4.3.8.1 were updated to reflect how medical history and concomitant medications will be coded.
- Section 4.3.10 was added to give details of intercurrent HAE attacks.
- Section 6.7.1, 6.7.2 and 6.7.3 were updated to indicate that the relevant summaries will be by primary attack first, and then by anatomical location.
- Section 6.7.5 was updated to better reflect the output it describes.
- Section 6.7.6 was added to give details of a summary of those patients who receive a second dose of study medication.
- Section 6.8.1 was updated to better reflect the output it originally described and to include description of an additional output "Total Exposure to rhC1INH".
- Section 6.8.2 was updated to describe in more detail the AE related summaries including the addition of three new tables.
- Section 6.8.8 was updated to better describe immunogenicity related outputs.
- Section 6.9.1 was updated to include description of a new shift table of IgE.
- Section 6.9.2 was updated with more detail and to reflect the change in the output summaries to be produced.
- The following tables were removed from the list of tables, listings and figures:
  - Summary of PK/PD Concentrations
  - Summary of PK/PD Parameters
- The following tables were added to the list of tables, listings and figures:
  - Receipt of a Second Dose of rhC1INH
  - Functional C1INH (% of Normal) Over Time
  - Functional C1INH (% of Normal) Cmax and AUC(0-3) Parameters
  - C4 Concentrations Over Time
  - Incidence of Related Treatment-Emergent Adverse Events
  - Incidence of Treatment-Emergent Adverse Events Commencing Within 24 Hours of the Completion of the Infusion of Study Drug Administration
  - Incidence of Treatment-Emergent Adverse Events Commencing Within 28 Days of the Completion of the Infusion of Study Drug Administration
  - Change in Status of Hematology Laboratory Parameters Based on Laboratory Reference Ranges from Presentation of Attack to Day 28
  - Change in Status of Biochemistry Laboratory Parameters Based on Laboratory Reference Ranges from Presentation of Attack to Day 28
  - Total exposure to rhC1INH
  - Shift Table of IGE
- The following listings were removed from the list of tables, listings, and figures:
  - Listing of Immunogenicity Data
- The following listings were added to the list of tables, listings and figures:
  - Initial ELISA Immunology Results
  - Neutralizing and Displacement Assay Immunology Results
  - Initial ELISA Immunology Results – Patients with a Confirmed Positive Result

- Neutralizing and Displacement Assay Immunology Results – Patients with a Confirmed Positive Result
- The following figures were removed from the list of tables, listings and figures:
  - Bar Chart of IS Score by Time, Attack Number and Attack Location
  - Median PK/PD Concentrations (Linear Scale)
  - Median PK/PD Concentrations (Logarithmic Scale)
  - PK/PD Concentrations by Patient (Linear Scale)
  - PK/PD Concentrations by Patient (Logarithmic Scale)
- The following figures were added to the list of tables, listings and figures:
  - Boxplot of Functional C1INH (% of Normal) paneled by Time (Linear Scale)
  - Boxplot of Functional C1INH (% of Normal) paneled by Time (Logarithmic Scale)
  - Boxplot of Functional C1INH (% of Normal) grouped by Weight and paneled by Time (Linear Scale)
  - Boxplot of Functional C1INH (% of Normal) grouped by Weight and paneled by Time (Logarithmic Scale)
  - Boxplot of C4 Concentrations paneled by Time (Linear Scale)
  - Boxplot of C4 Concentrations paneled by Time (Logarithmic Scale)
  - Boxplot of C4 Concentrations grouped by Weight and paneled by Time (Linear Scale)
  - Boxplot of C4 Concentrations grouped by Weight and paneled by Time (Logarithmic Scale)
  - Ratio with respect to Baseline in C4 versus Ratio with respect to Baseline in Functional C1INH

#### **7.4 Changes from the Statistical Analysis Plan Version 3.0.0**

- The definition of eligible location was updated to be based on the IS score as per protocol rather than Overall VAS score.
- The definition of Therapeutic Failure was updated to be consistent with that of Disallowed Medication in Section 4.1.1.6.
- The definition of how to deal with values below the lower limit of quantification for diagnostic parameters, IM, PK and PD concentrations was updated.
- It was clarified that time to event results censored before exposure to treatment due to Disallowed Medication would be censored at 0 minutes.

